9.1.3. Analysis of Efficacy effects

To assess whether VVN001 is more effective than Vehicle, exploratory efficacy will be performed. The unit of analysis for ophthalmic efficacy measures depends on the measure itself. Some endpoints will be analyzed per subject whereas others will be analyzed per eye (study eye and non-study eye, where study eye is defined in Section 4.4).

The following parameters will be assessed per eye (study eye and non-study eye):

- Total and Individual CFS score
- Tear production (Schirmer test without anesthesia, mm/5 min)

The following parameters will be assessed per subject (one score for both eyes):

- VAS for Eye Discomfort
- VAS for Eye Dryness
- SANDE

All efficacy parameters will be analyzed as continuous data. Analysis will be performed at each timepoint using summary statistics as well as a longitudinal model as appropriate.

Analyses of all efficacy endpoints will be done using the FAS. Analyses on the study eye will be repeated for all non-study eye as supportive analyses. Analyses may also be repeated on the PP set.

The primary analysis will utilize a repeated measures mixed model where the dependent variable is the change from baseline score, treatment group is a fixed effect, baseline score is a covariate, and visit is a repeated measure on subject. The repeated measures mixed model is utilized to account for the effect of missing data under the assumption that the data are missing at random. Least squares means will be used to test each concentration of VVN001 to vehicle. Sensitivity analyses for the primary endpoint will be performed using last observation carried forward (LOCF) as well as observed data only.

In order to minimize the impact of multiplicity, the following hierarchical tests will be conducted:

- 1) Primary (iCFS on Day 84, study eye) high concentration vs. vehicle
- 2) Primary (iCFS on Day 84, study eye) low concentration vs. vehicle
- 3) Key secondary (Eye Dryness VAS on Day 84) high concentration vs. vehicle
- 4) Key secondary (Eye Dryness VAS on Day 84) low concentration vs. vehicle

The comparisons will be conducted at the 5% significance level. Each comparison will be made in order until $P > 0.05$. If $P \leq 0.05$, the comparison is statistically significant and testing is continued.

The planned analyses for all outcomes will be described in detail in the SAP, which will be finalized and submitted prior to database lock.

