4.2.4. Adjustments for Covariates

Analyses of the change from baseline in primary and secondary efficacy endpoints utilizing repeated measures mixed model will adjust for the baseline score of the parameter of interest as a continuous covariate, treatment group as the main effect, and visit as a repeated measure on subject in the model.

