4.7.1. Primary Analyses

The primary comparisons in this trial will be VVN001 5% versus vehicle and VVM001 1% versus vehicle on Day 84 in CFB of iCFS score on study eye. The repeated measures mixed model will be utilized to compare the treatment group. This method will assume that any missing data is Missing at Random (MAR). The repeated measures are the absolute change from baseline iCFS score obtained at the scheduled visit Day 14, 28, 56 and 84 respectively. The model will include treatment group (VVN001 5%, VVN001 1% and vehicle), baseline iCFS score, visit (Day 14, 28, 56 and 84), the interaction term of treatment \times visit as fixed effects, the center as a random effect.

SAS *PROC MIXED* with restricted maximum likelihood estimation (REML) and an unstructured (UN) within-subject covariance structure will initially be used. The sample SAS analysis code will use the following structure:

```
PROC MIXED DATA=indata;
  CLASS subject center visit treatment (REF='Vehicle');
```

Sponsor:	VivaVision Biotech, Inc.		
Protocol:	VVN001-CS-201		
Document Version No.:	V3.0	Document Date:	13-JAN-2022

```

MODEL change = treatment visit baseline_value treatment * visit
/Solution DDFM=KR;
  REPEATED visit / SUBJECT=subject TYPE=UN;
  RANDOM center;
  LSMEANS treatment treatment * visit / PDIFF CL;
  SLICE treatment * visit / SLICEBY=visit PDIFF CL;
RUN;

```

If the model fails to converge, compound symmetry (CS) will be implemented. From this model, the least squares mean (LSMEANS) for each treatment group and the estimated treatment differences for treatment comparisons will be presented together with 95% 2-sided confidence intervals for the differences and two-sided p-values for the treatment comparisons of the overall analysis. For assessments performed by eye, study eye and non-study eye will be summarized separately.

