4.7.2. Secondary Analyses

The secondary efficacy endpoints listed below will be analyzed using repeated measure mixed model by adjusting for covariates that include treatment group, baseline value, visit and interaction term of treatment * visit as the fixed effects. The center will be considered as random effect. The treatment group comparison for each secondary endpoint at each timepoint (Day 84, Day 56, Day 28 and Day 14) will be tested using hierarchical fixed sequence testing followed by the sequential order below:

Statistical Analysis Plan

Sponsor:	VivaVision Biotech, Inc.		
Protocol:	VVN001-CS-201		
Document Version No.:	V3.0	Document Date:	13-JAN-2022

- CFB in eye dryness VAS on Day 84
- CFB in total CFS (tCFS) on Day 84, Day 56, Day 28, Day 14
- CFB in inferior of CFS (iCFS) on Day 56, Day 28, Day 14
- CFB in nasal of CFS on Day 84, Day 56, Day 28, Day 14
- CFB in temporal of CFS on Day 84, Day 56, Day 28, Day 14
- CFB in central of CFS on Day 84, Day 56, Day 28, Day 14
- CFB in superior of CFS on Day 84, Day 56, Day 28, Day 14
- CFB in eye dryness VAS on Day 56, Day 28, Day 14
- CFB in eye discomfort VAS on Day 84, Day 56, Day 28, Day 14
- CFB in SANDE global score on Day 84, Day 56, Day 28, Day 14
- CFB in Schirmer test result on Day 84, Day 56, Day 28, Day 14

For each sequential order of endpoint and each timepoint, the least squares mean (LSMEANS) for each treatment group and the estimated treatment differences for the treatment comparisons (VVN001 5% vs. vehicle and VVM001 1% vs. vehicle) will be reported together with two-sided p-values and 95% 2-sided confidence intervals. The endpoints on study eye and non-study eye will be summarized in the separate model.

The sample code of SAS *PROC MIXED* would be:

```
PROC MIXED DATA=indata;
  CLASS subject center visit treatment(REF='Vehicle');
  MODEL change = treatment visit baseline_value treatment * visit
    /Solution DDFM=KR;
  REPEATED visit / SUBJECT=subject TYPE=UN;
  RANDOM center;
  LSMEANS treatment treatment * visit /PDIFF CL;
  SLICE treatment * visit / SLICEBY=visit PDIFF CL;
RUN;
```

The model convergence and the choice of covariance structure will be handled as similar to the primary analyses mentioned in section 4.7.1.

In addition, the frequency and percentage of subjects achieving a 10-milimeter increase or more in Schirmer test scores from baseline will be presented at each post-baseline visit and any visits

Sponsor:	VivaVision Biotech, Inc.		
Protocol:	VVN001-CS-201		

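### The mixed models hold the baseline slope constant over Days 14–84; a pre-specified baseline-by-visit term is cheap protection for the Day 84 contrast if that slope changes over time

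*SAP*

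**What the plan says.** SAP 4.7.1 models the change in study-eye iCFS "obtained at the scheduled visit Day 14, 28, 56 and 84 respectively". Its code has "MODEL change = treatment visit baseline_value treatment * visit", with center random. On the covariance, it says "restricted maximum likelihood estimation (REML) and an unstructured (UN) within-subject covariance structure will initially be used"; compound symmetry is the fallback if the model does not converge. Missing data are assumed missing at random.

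SAP 4.7.2 gives the same terms for the secondary endpoints: "treatment group, baseline value, visit and interaction term of treatment * visit as the fixed effects". SAP 4.2.4 says the analyses "will adjust for the baseline score of the parameter of interest as a continuous covariate". Protocol 9.1.3 describes the same kind of model, in which "treatment group is a fixed effect, baseline score is a covariate, and visit is a repeated measure on subject".

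So baseline enters as a main effect everywhere, and the only interaction is treatment by visit. Neither document includes a baseline-by-visit term or says why it is left out. The one specified analysis with its own Day 84 baseline slope is the ANCOVA in SAP 4.7.1.1, and that uses LOCF data.

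**The concern.** With treatment by visit and an unstructured covariance, the model is flexible by visit in every respect except the baseline slope. Because the outcome is change from baseline, the slope at a visit depends on how strongly the score at that visit still tracks the Visit 2 score. If that tracking weakens over 12 weeks, the change-score slope is steeper at Day 84 than at Day 14. A single slope then settles between the two and adjusts Day 84 too little.

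Day 84 matters most because the fixed sequence in SAP 4.2.5 starts with the 5% versus vehicle contrast in iCFS at Day 84 and stops at the first p-value above 0.05. Any power lost there is lost for every later test.

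There is a second, narrower issue. A likelihood analysis under missing at random relies on a correct mean model at each visit. A wrong Day 84 slope could shift the Day 84 contrast if the arms lose subjects with different baseline scores.

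Subjects are selected on Visit 2 values (iCFS of at least 2, dryness of at least 35, and the worse-staining eye when both qualify), so baseline is likely to be related to change. That does not show that the relationship differs between visits.

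**Working it through.** **Plan's own figure.** SAP 4.1 gives 55 per group, a difference of 0.43, SD 0.80 and a two-sided 0.05 t-test. The noncentrality is 0.43 / (0.80 × √(2/55)) = 2.82, and power is 79.8% (80.5% by normal approximation). For eye dryness (13.75, SD 25.5) it is 80.0%. The stated 80% reproduces.

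**Assumed inputs.** The documents give no baseline SD, no correlations and no dropout rate. I assume baseline SD 0.5, SD 0.80 for the follow-up score at each visit, and between-visit correlation 0.7.

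**Formulas.**
- Change-score slope at visit v: β_v = ρ_v × 0.80/0.5 − 1, where ρ_v is the correlation of the visit score with baseline.
- Day 84 residual variance with the correct slope: 0.64 × (1 − ρ₈₄²).
- Common slope: b = Σ w_v β_v, with generalized least squares weights w = 1′S⁻¹ / (1′S⁻¹1), where S is the residual covariance.
- Day 84 variance inflation: 1 + (β₈₄ − b)² × 0.25 / residual variance.

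**Strong fall, ρ = 0.6, 0.5, 0.4, 0.3.**
- Slopes: −0.04, −0.20, −0.36, −0.52. Residual variance: 0.64 × 0.91 = 0.5824 (SD 0.763).
- Same correlation of 0.7 between all visit pairs: weights 0.52, 0.34, 0.16, −0.02, so b = −0.136. Inflation = 1 + 0.384² × 0.25/0.5824 = 1.063.
- Correlation of 0.7 between adjacent visits, decaying with distance: b = −0.227. Inflation = 1 + 0.293² × 0.25/0.5824 = 1.037.
- Power by noncentral t: 83.4% with visit-specific slopes; 81.1% (inflation 1.063) to 82.0% (inflation 1.037) with the common slope.
- Spacing the fall by study day instead (0.6, 0.54, 0.42, 0.3), with constant correlation: b = −0.096. Inflation = 1 + 0.424² × 0.25/0.5824 = 1.077 and power is 80.6%, still above 80%.

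**Mild fall, ρ = 0.6, 0.55, 0.5, 0.45.** Residual variance is 0.64 × 0.7975 = 0.5104 and b = −0.123. Inflation = 1 + 0.157² × 0.25/0.5104 = 1.012. Power is 87.9% against 87.5%.

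**Simulation check** (20,000 complete-data trials per scenario, 3 × 55 subjects, center omitted). Strong fall: variance 6.4% higher (5.7% model-based), power 81.3% against 83.3%. Mild fall: about 1%. Equal slopes: the extra term costs 0.2–0.6%.

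**Bias check** (600 trials per scenario; change slopes set directly; true Day 84 difference −0.43; dropout odds ratio 2.7 per baseline SD). The entries are the common-slope estimate minus the baseline-by-visit estimate, in iCFS units; n/r means not run.

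| Slopes, Day 14 to 84 | Alike in all arms, 10% dropout | Opposite by arm, 10% | Opposite by arm, 20% |
|---|---|---|---|
| −0.4 throughout | −0.0003 | −0.0003 | −0.002 |
| −0.2 to −0.5 | 0.0007 | −0.020 | −0.033 |
| −0.1 to −0.7 | 0.0006 | −0.037 | −0.063 |
| Largest Monte Carlo SE | 0.0011 | 0.0012 | 0.0017 |

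Against the design effect, 0.063/0.43 = 15%. A separate adverse run (19% dropout after Day 28, opposite directions by arm) gave bias of about 0.075 with the common slope and about 0.01 with the interaction (Monte Carlo error about 0.01).

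**The case against.** A common baseline slope is a valid and widely used specification, and it agrees with Protocol 9.1.3. With equal slopes it loses nothing, and no figure in the documents shows that they are unequal. The trial is Phase 2a, and the protocol calls its efficacy analysis exploratory. The LOCF ANCOVA gives a partial check, and SAP 4.2.8.1 also promises an observed-data sensitivity analysis, although its model is not specified. All of this stands and limits the point to a robustness improvement. The LOCF ANCOVA does not settle the question, because a disagreement with the primary model could come from the slope or from LOCF.

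Three stronger readings are tempting, and the documents do not support them.

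- **That the plan certainly loses precision.** The loss is conditional on slopes that differ by visit.
- **That power falls below 80%.** A reader might apply the inflation to the t-test's 79.8% and arrive near 77.5%. That treats 0.80 as the SD left after baseline adjustment. SAP 4.1 gives it as the common SD for an unadjusted t-test and does not call it a residual SD. If 0.80 is the follow-up SD, both models gain from adjustment and the planned one stays above 80% in the complete-data scenarios here.
- **That any baseline-related dropout biases the contrast.** When the dependence is alike in all arms, the shift cancels.

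**Conclusion.** The point holds as a conditional one. The cost of the common slope in Day 84 variance is nil with equal slopes, about 1% for a mild fall in the baseline correlation, and about 4–6% for a strong fall in equal steps per visit. The last is worth about 2 power points (83.4% to 81.1%, no dropout). Bias requires slopes that differ by visit and baseline-related dropout that differs by arm. It was about 0.02–0.075 units in scenarios built to be adverse, and its sign depends on which arm loses the higher baselines. The documents give no evidence that either condition applies. All sizes rest on the assumed SDs, correlations and dropout patterns. The trade still favors the extra term: it costs well under 1% if it is not needed and recovers more than that if it is. The planned analysis is not invalid, and the stated sample size is unaffected.

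**What to change.** In SAP 4.7.1 and 4.7.2, for all endpoints modelled this way, use `MODEL change = treatment visit treatment*visit baseline_value baseline_value*visit`, and state in 4.2.4 that the baseline effect may differ by visit. The Day 84 contrast is read from the same LSMEANS and SLICE output as now: within a visit the slope is shared by the arms, so the treatment difference does not depend on the baseline value at which it is evaluated. If the sponsor prefers the common slope, one sentence should justify it.

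The cost is one term in the code (3 degrees of freedom) and one SAP sentence. The change should be made before unmasking, because adding the term later would look data-driven. If unmasking has already taken place, the model with the interaction should be reported only as a labelled supportive analysis.

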4.2. General Statistical Methods and Data Handling

4.2.1. General Methods

All output will be incorporated into Microsoft Excel or Word files, sorted and labeled according to the International Conference on Harmonisation (ICH) recommendations, and formatted to the appropriate page size(s).

Tabulations will be produced for appropriate demographic, baseline, efficacy and safety parameters. For categorical variables, summary tabulations of the number and percentage within each category (with a category for missing data) of the parameter will be presented by treatment group and visit (as applicable). For continuous variables, the sample size (n), mean, median, standard deviation, minimum and maximum values will be summarized by treatment group and visit (as applicable). All study data will be listed by treatment group, subject and visit (as applicable).

Formal statistical hypothesis testing will be performed on the primary and secondary efficacy endpoints with all tests conducted at the 2-sided, 0.05 level of significance.

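### Compound symmetry is the only named fallback if the unstructured model fails; wherever it is used, it gives wrong visit-specific standard errors if the variance differs by visit

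*SAP*

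**What the plan says.** SAP section 4.7.1 analyses the change from baseline in iCFS "obtained at the scheduled visit Day 14, 28, 56 and 84 respectively". The primary comparison is "VVN001 5% versus vehicle and VVM001 1% versus vehicle on Day 84 in CFB of iCFS score on study eye". Under REML, "an unstructured (UN) within-subject covariance structure will initially be used", and the model statement carries "Solution DDFM=KR", so the standard errors are model-based with the Kenward-Roger adjustment. Center enters as a random effect. The plan for failure is one sentence: "If the model fails to converge, compound symmetry (CS) will be implemented". No intermediate structure and no sandwich standard error is named.

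Section 4.7.2 extends this to the secondary endpoints: "The model convergence and the choice of covariance structure will be handled as similar to the primary analyses". Section 4.2.1 has formal testing "with all tests conducted at the 2-sided, 0.05 level of significance", and section 4.2.5 puts the 5% concentration against vehicle on Day 84 iCFS first in the fixed sequence. Protocol section 9.1.3 names a repeated measures mixed model but no covariance structure.

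**The concern.** The unstructured matrix for four visits has 10 free parameters: four variances and six covariances. Compound symmetry has two, one variance and one correlation. The fallback therefore gives up the visit-specific variances in a single step, although structures that keep them with fewer parameters exist.

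This matters because the tests concern single visits. Under compound symmetry the standard error of the Day 84 contrast is built from the average variance over all four visits. If the spread of the change scores is larger at Day 84 than on average, that standard error is too small, the confidence interval too narrow, and the test rejects too often. Kenward-Roger corrects for small-sample uncertainty within the chosen structure; it does not repair a wrong structure. Were this to happen in the primary model, the first test in the hierarchy would not hold its stated level.

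**Working it through.** **Inputs from the documents.** 55 subjects per group; iCFS difference 0.43 with SD 0.80; eye dryness difference 13.75 with SD 25.5; two-sided 0.05 (SAP section 4.1, protocol section 9.1.5). Four post-baseline visits (SAP section 4.7.1).

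**Assumptions.** The documents give one SD per endpoint and none for Days 14, 28 or 56, so the earlier SDs below are assumed. The sample size section does not say that 0.80 is the SD of the change score; I take it as such. The formula assumes complete data.

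**The plan's own figure.** SE of the iCFS difference = 0.80 × √(2/55) = 0.1526. Power = Φ(0.43/0.1526 − 1.96) = 80.5% by the normal approximation and 79.8% by the exact t. For eye dryness the results are 80.7% and 80.0%. The stated 80% is reproduced.

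**Size under compound symmetry.** With complete data:

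- model SE at any visit = √(mean of the four visit variances) × √(2/55)
- true SE at visit v = SD_v × √(2/55)
- ratio r = √(mean variance) / SD_v
- actual size = 2 × [1 − Φ(1.96 × r)]

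Worked example, SDs 0.50/0.60/0.70/0.80: mean variance = (0.25 + 0.36 + 0.49 + 0.64)/4 = 0.435, with square root 0.6595. At Day 84, r = 0.6595/0.80 = 0.824, the model SE is 0.1258 against a true 0.1526, and the size is 2 × [1 − Φ(1.616)] = 10.6%.

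| Assumed SD at Days 14/28/56/84 | r at Day 84 | Size at Day 84 |
|---|---|---|
| 0.80/0.80/0.80/0.80 | 1.000 | 5.0% |
| 0.70/0.73/0.77/0.80 | 0.939 | 6.6% |
| 0.60/0.67/0.73/0.80 | 0.880 | 8.5% |
| 0.50/0.60/0.70/0.80 | 0.824 | 10.6% |
| 0.95/0.90/0.85/0.80 (falling) | 1.096 | 3.2% |

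**The other visits, SDs 0.50/0.60/0.70/0.80.** Day 14: r = 0.6595/0.50 = 1.319, size 1.0%. Day 28: r = 1.099, size 3.1%. Day 56: r = 0.942, size 6.5%. The same pooled variance makes the late tests liberal and the early tests conservative.

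**Check by simulation.** REML fits were simulated with 3 × 55 subjects, treatment-by-visit and baseline terms, 10% dropout and a correlation decaying as 0.6 per 28 days (both assumed); the center effect was left out. Day 84 size under compound symmetry was 4.9% with equal SDs, 6.6% with 0.70/0.74/0.77/0.80 (6.5% by the formula), 8.9% with 0.60/0.67/0.73/0.80, 11% to 12% with 0.50/0.60/0.70/0.80, and 3.0% with the falling pattern. In the 0.50 to 0.80 case, the unstructured model gave 5.4% with a mean SE of 0.159, against an empirical SD of about 0.16; compound symmetry gave a mean SE of 0.130.

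**The case against.** The strongest reply is that the fallback will probably never be used where it matters most. The unstructured matrix has 10 parameters for about 165 subjects at four visits, so failure is unlikely for iCFS. No convergence rate has been estimated for any endpoint, and the idea that the random center effect or subregion scores near zero would cause failures is untested. This stands, and it keeps the point minor.

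Two stronger readings are tempting. A reader might infer that once the fallback is used, it governs the Day 84 primary test and every secondary test together. The SAP ties the switch to failure of the model being fitted, so a failed subregion model leaves iCFS and eye dryness on the unstructured fit. A reader might also infer that the error always inflates type I error if variance rises. The Day 14 and Day 28 results above show otherwise.

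Reach is limited too. The table list implies 34 fits: seven per-eye endpoints × 2 eyes + 3 subject-level endpoints = 17, on both FAS and PPS. But the protocol calls the non-study-eye analyses supportive, the PPS fits repeat the FAS ones, and subregions enter formal testing only if all four primary and key secondary comparisons succeed.

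Finally, the plan has checks that use one visit's variance at a time: SDs and two-sample tests by visit (SAP section 4.7) and the Day 84 ANCOVA with LOCF (section 4.7.1.1). They could expose a distortion. They do not remove it, because section 4.2.5 makes the mixed model the deciding test, and the LOCF analysis covers iCFS only and brings its own missing-data assumption.

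**Conclusion.** The point holds as a conditional weakness, and correcting it is an optional improvement. In any model where the fallback is used, the visit-specific standard errors are wrong if the variance differs by visit. Over the patterns tabulated, the true size of the nominal 5% Day 84 test runs from about 3% to about 11%, with inflation only if the Day 84 variance exceeds the average over visits. A rising variance of change scores is plausible, but nothing in the documents establishes it, and equal variances leave the size at 5%. The documents do not support saying that the primary test is inflated as planned: with the unstructured model it is not affected.

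**What to change.** Replace the fallback sentence in SAP section 4.7.1 with a fixed order of structures that keep visit-specific variances: heterogeneous Toeplitz, then heterogeneous first-order autoregressive (ARH(1)), then heterogeneous compound symmetry (CSH). The first that converges is used, model by model, and plain compound symmetry is the last resort. The cross-reference in section 4.7.2 then carries the new order to the secondary models.

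If plain compound symmetry is reached, use empirical (sandwich) standard errors. These cannot simply be added to the sample code. The SAP should state that DDFM=KR is replaced by another named degrees-of-freedom method, and that the random center term is removed or otherwise handled so that the model is blocked by subject.

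The cost is a few lines of SAP text and some programming. The sample size is unchanged, and no result changes if the unstructured model converges.

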4.2.5. Multiple Comparisons/Multiplicity

To avoid inflation of the type I error rate due to multiple hypotheses, the analysis of primary and key secondary efficacy endpoints will be conducted in the following hierarchical tests:

- 1) Primary (iCFS on Day 84, study eye) high concentration vs. vehicle
- 2) Primary (iCFS on Day 84, study eye) low concentration vs. vehicle
- 3) Key secondary (Eye Dryness VAS on Day 84) high concentration vs. vehicle
- 4) Key secondary (Eye Dryness VAS on Day 84) low concentration vs. vehicle

The comparisons will be conducted by using the repeated measure mixed model at the 5% significance level. Each comparison will be made in order until 2- sided p value > 0.05 . If p value ≤ 0.05 , then comparison is statistically significant, and testing is continued.

If both primary and key secondary efficacy endpoints demonstrate statistically significant superiority of each concentration of VVN001 versus vehicle at the two-sided 5% level, the similar hierarchical tests defined above will be conducted for the other secondary efficacy endpoints in the order of Day 84, Day 56, Day 28, Day 14 and in the order of presentation high concentration, low concentration within each endpoint specified in Section 2.4.2.2.

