4.7.1.1. Sensitivity Analyses

Sensitivity analyses will be performed on the FAS population by using last observation carried forward (LOCF) imputation methodology to compare the treatment group on Day 84. LOCF will be used to impute missing data for the analysis of covariance (ANCOVA) model with terms for baseline iCFS score and treatment group as covariate. The model assumptions such as Shapiro-Wilk's test of normality; Levene's test of homogeneity of variance will be validated. The estimates of least squares mean for each treatment group and for the difference between treatment groups will be presented together with 95% confidence intervals and two-sided p-value. The sample SAS ANCOVA code would be:

```

PROC GLM DATA= indata;
  CLASS treatment(REF='Vehicle');
  MODEL change = treatment baseline_value;
  LSMEANS treatment / PDIFF CL;
RUN;

```

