7. CLINICAL STUDY REPORT APPENDICES

7.1. Statistical Tables to be Generated

Tables

Number	Title
Table 14.1.1	Overall Disposition and Subject Accountability – All Subjects Screened
Table 14.1.2	Overview of Analysis Sets – All Subjects Randomized
Table 14.1.3	Major Protocol Deviations – FAS
Table 14.1.4	Demographic and Baseline Characteristics - FAS
Table 14.1.5	Ocular Characteristics at Screening - FAS
Table 14.1.6.1	Study Eye Ocular Medical History - FAS
Table 14.1.6.2	Non-Study Eye Ocular Medical History – FAS
Table 14.1.6.3	Subject Level (Both Eyes) Ocular Medical History - FAS
Table 14.1.6.4	Non-ocular Medical History – FAS
Table 14.1.7.1	Study Eye Ocular Prior Concomitant Medications - SAF
Table 14.1.7.2	Non-Study Eye Ocular Prior Concomitant Medications – SAF
Table 14.1.7.3	Subject Level (Both Eyes) Prior Ocular Concomitant Medications – SAF
Table 14.1.7.4	Non-ocular Prior Concomitant Medications – SAF
Table 14.1.7.5	Study Eye Ocular Concomitant Medications – SAF
Table 14.1.7.6	Non-Study Eye Ocular Concomitant Medications – SAF
Table 14.1.7.7	Subject Level (Both Eyes) Ocular Concomitant Medications - SAF
Table 14.1.7.8	Non-ocular Concomitant Medications – SAF
Table 14.1.8	Study Medication Exposure - SAF
Table 14.2.1.1	Summary of Individual Subregion of CFS and Change from Baseline on Study Eye by Visit – FAS
Table 14.2.1.2	Summary of Individual Subregion of CFS and Change from Baseline on Study Eye by Visit - PPS
Table 14.2.1.3	Summary of Individual Subregion of CFS and Change from Baseline on Non-Study Eye by Visit - FAS
Table 14.2.1.4	Summary of Individual Subregion of CFS and Change from Baseline on Non-Study Eye by Visit - PPS
Table 14.2.2.1	Repeated Measures Mixed Model for Change from Baseline (CFB) in Inferior Region of CFS (iCFS) on Study Eye on Day 84 – FAS
Table 14.2.2.2	Repeated Measures Mixed Model for Change from Baseline (CFB) in Inferior Region of CFS (iCFS) on Study Eye on Day 84 – PPS

Sponsor:	VivaVision Biotech, Inc.		
Protocol:	VVN001-CS-201		
Document Version No.:	V3.0	Document Date:	13-JAN-2022

Table 14.2.2.3	Repeated Measures Mixed Model for Change from Baseline (CFB) in Inferior Region of CFS (iCFS) on Non-Study Eye on Day 84 – FAS
Table 14.2.2.4	Repeated Measures Mixed Model for Change from Baseline (CFB) in Inferior Region of CFS (iCFS) on Non-Study Eye on Day 84 – PPS
Table 14.2.2.5	Sensitivity Analysis: ANCOVA with LOCF Imputation for Change from Baseline (CFB) in Inferior Region of CFS (iCFS) on Day 84 – FAS

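### Does the SAP leave open whether the primary iCFS test is at Day 84 or averaged over visits?

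*SAP*

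**What the plan says.** SAP 4.7.1 opens by defining the primary comparisons as each concentration "versus vehicle on Day 84 in CFB of iCFS score on study eye". It fits change from baseline at Days 14, 28, 56 and 84. Treatment, visit, baseline iCFS and treatment-by-visit are fixed effects, with "the center as a random effect". The sample code contains "LSMEANS treatment treatment * visit / PDIFF CL" and a SLICE statement by visit. The closing sentence promises LS means per treatment group, estimated differences with 95% intervals, and "two-sided p-values for the treatment comparisons of the overall analysis".

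SAP 4.2.5 makes step 1 of the hierarchy "Primary (iCFS on Day 84, study eye) high concentration vs. vehicle". Step 2 is the same endpoint and visit for the low concentration, and both steps use the mixed model. Protocol 9.1.3 lists the same steps.

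SAP 4.2.4 and protocol 9.1.3 describe the mixed model more briefly: treatment, baseline score, and visit as the repeated measure. Neither mentions treatment-by-visit or center. SAP 5 records no change from the protocol-defined analyses.

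**The concern.** In a model with treatment-by-visit, the plain treatment LS means average over the four visits, and *overall* is a natural label for that output. The matching sentence in SAP 4.7.2 is more careful: "For each sequential order of endpoint and each timepoint, the least squares mean (LSMEANS) for each treatment group". So the endpoint that gates all the others seems to have the looser reporting rule. Read literally, SAP 4.2.4 and protocol 9.1.3 go further. A model with no interaction has a single treatment difference common to all visits, and so no separate Day 84 estimate.

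The stakes would be real. A visit average understates an effect that builds up late, and it can reach significance on an early effect that has gone by Day 84. If either contrast could be chosen after the data were seen, the type I error at step 1 would exceed 5%. SAP 5 adds to the unease, because the interaction and the center effect do not appear in the protocol's model and are not listed as changes.

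**Working it through.** **1. Which contrast do the documents name?**

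| Place | What it fixes |
|---|---|
| Protocol 9.1.3 and SAP 4.2.5, hierarchy | iCFS, Day 84, study eye |
| Protocol 9.1.5 and SAP 4.1, sample size | Visit 6/Day 84 |
| SAP 4.7.1, opening sentence | Day 84 |
| SAP 4.7.1, model and code | interaction fitted; differences requested at each visit |
| SAP 4.7.1.1, ANCOVA | LOCF "imputation methodology to compare the treatment group on Day 84" |
| SAP 7.1, Table 14.2.2.1 | "Repeated Measures Mixed Model for Change from Baseline (CFB) in Inferior Region of CFS (iCFS) on Study Eye on Day 84" |
| SAP 7.1, Tables 14.2.2.2 to 14.2.2.5 | Day 84 in each title |
| SAP 4.7.1, closing sentence | no visit named |
| SAP 4.2.4 and protocol 9.1.3, model summary | no interaction named |

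No entry names a visit average. The other mixed-model tables in SAP 7.1 (14.2.8.1 to 14.2.13.4) are titled by visit, so no planned table title is for a visit-averaged result.

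**2. The plan's own figure.** Inputs from SAP 4.1: 55 per arm, difference 0.43, SD 0.80, two-sided 0.05, t-test.

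- SE = 0.80 × √(2/55) = 0.1526
- 0.43 / 0.1526 = 2.819
- Power from the noncentral t with 108 degrees of freedom = 79.8% (80.5% by the normal approximation)

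The stated 80% reproduces, and it applies to the Day 84 contrast.

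**3. What a visit average would do.** The documents give no correlation or time course, so these are assumptions: SD 0.80 at every visit, complete data, equal correlation ρ of 0.4 to 0.6 between visits, and equal weights (the plain treatment LS means).

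- SD of a four-visit mean = 0.80 × √((1 + 3ρ)/4) = 0.593 at ρ = 0.4 and 0.669 at ρ = 0.6
- SE = 0.113 and 0.128

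| Assumed effect at Days 14, 28, 56, 84 | Visit average | Rejection rate, ρ 0.4 to 0.6 |
|---|---|---|
| 0.072, 0.143, 0.287, 0.43 (linear in day) | 0.233 | 53% to 44% |
| 0.43 throughout | 0.43 | 96% to 92% |
| 0.43, 0.43, 0.20, 0 (early only) | 0.265 | 64% to 54% |

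Free choice between the two contrasts would give a step 1 type I error of about 8.4% to 7.2% for ρ from 0.3 to 0.7.

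**4. Limits of these figures.** They cover only the equal-weight reading. A no-interaction model with the SAP's first-choice unstructured covariance weights visits by the inverse covariance. With correlation decaying over time (assumed 0.4 to 0.8 per 28 days), Day 84 gets a weight of 0.34 to 0.44. The linear-pattern average becomes about 0.25, and early-only rejection is 60% to 37%. Both sets describe tests that appear in no hierarchy step.

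**The case for a change.** The strongest case for an edit is that intent should not have to be inferred. A prespecified gate ought to identify one contrast. Here the code produces two families of differences, the sentence after it says *overall*, and SAP 4.2.4 disagrees with 4.7.1 inside the same document. A few words would cure it, at no cost to sample size, data or tables.

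What stands is textual: the sentence is loose, 4.2.4 is incomplete, and SAP 5 is silent about the center effect and the explicit interaction.

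The step from there to a wrong test does not stand:

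- The treatment comparisons at the end of 4.7.1 refer back to the primary comparisons defined in its first sentence, which are at Day 84. Section 4.7.2 spells out timepoints because it covers up to four visits per endpoint; the primary has one.
- Elsewhere the SAP uses *overall* for pooled treatment groups and never defines it as pooling visits.
- Section 4.2.4 is a summary headed for covariate adjustment. To fit its literal model, a programmer would have to set aside the full model and code in 4.7.1.
- Protocol 9.1.3 itself lists the Day 84 tests and leaves analysis detail to the SAP. The interaction is what makes those tests possible, so it supplies detail and does not replace the analysis.
- SAP 1.1 promises to outline differences in analytical objectives, and these are unchanged. The center effect is a genuine omission from SAP 5, but it does not alter which contrast is tested.

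**Conclusion.** The concern does not call for a change. The mismatches are real but clerical. An analyst following SAP 4.2.5, the model and code in 4.7.1, and the table titles will report the Day 84 treatment-by-visit difference for each concentration against vehicle and carry it into steps 1 and 2. Tidier wording would leave that analysis and its result as they are.

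The planned power for iCFS, 79.8% at 55 per arm under the SAP's own difference and SD, is unaffected. The losses and false signals shown for a visit average depend on assumed correlations and time courses, and they arise only if several explicit Day 84 statements are overridden by one loose phrase. The conclusion rests on the text and not on those assumptions: Day 84 is named wherever the test is defined, and a visit average is assigned nowhere.
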